8.3.3.1.3. Sensitivity Analysis of Primary Endpoint

The following sensitivity analysis of the primary endpoint will be performed to assess the robustness of the primary analysis. For participants who terminate from treatment prior to the end of the analysis period for any of the following reasons: adverse event, noncompliance with study procedures, death, physician decision, or requires prohibited medication, missing measurements will be imputed as the worst post-baseline observation; for all other participants having missing measurements, missing values will be imputed with the last non-missing value before the scheduled visit time (LOCF principle).

If any of the sensitivity analyses yields a result that is in a different direction from the result of the primary analysis, the nature of the discrepancy will be examined to clearly explain the

discrepancy based on statistical principles and the discrepancy will be discussed in the clinical study report.

Another sensitivity analysis of primary endpoint will be performed to exclude the patients from the sites with potential risk of unblinding due to kit information accessed/downloaded, which is listed below:

8.3.3.1.4. Supportive Analysis of Primary and Secondary Endpoints

Summary of TETRAS performance subscale part 4 upper limb tremor total score (by side and combined), TETRAS performance total score, TETRAS performance subscale part 4/6/7/8 score, TETRAS ADL total score, and Kinesia ONE accelerometer total scores (by side and combined) along with model-based estimates and line plot will be provided for Per Protocol Set as a supportive analysis for the primary and secondary endpoint.

8.3.3.1.5. Subgroup Analyses of Primary and Key Secondary Endpoints

[figure not shown]
The TETRAS performance subscale part 4 upper limb tremor change from baseline total score (by side and combined), TETRAS performance total score, TETRAS performance subscale Part 4/6/7/8 score, and TETRAS ADL score will also be presented by the following subgroups:

- Age group: <65, 65-80 years
- Sex: Male, Female
- Race: White, Black or African American, Other
- BMI: <18.5, 18.5 - <25, 25-< 30, ≥ 30 kg/m²
- Age at essential tremor diagnoses: <40 years, 40-60 years, >60 years

- Age participant thinks essential tremor started: <40 years, 40-60 years, >60 years
- Years with essential tremor diagnosis: 3-<6 years, 6-10 years, and >10 years
- Years since participant thinks essential tremor started: 3-<6 years, 6-10 years, and >10 years
- Alcohol helps tremor: Yes (Intermediate, Worked Well), No (No, a little), NA
- Baseline TETRAS performance subscale part 4 upper limb tremor score: <12, >=12

If any of the subcategories has <5 patients fall into that category, that category should be combined with the next adjacent category with smaller counts. For example, if the number of patients fall into BMI category <18.5 is <5, this category should be combined with the 18.5 - <25 group.

Forest plots for subgroup analysis for change from baseline in TETRAS performance subscale part 4 upper limb tremor total score (by side and combined), TETRAS performance total score, TETRAS performance subscale Part 4/6/7/8 score, and TETRAS ADL total score at Day 29 – LS means, confidence interval – will be provided.

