8.3.3.1. Mixed Effects Model for Repeated Measures

8.3.3.1.1. Analysis of Primary Efficacy Variable

The estimand for the primary efficacy endpoints is defined as follows:

5. *There are two treatment regiments for participants to be evaluated: SAGE-324 or placebo.*
6. *The target population consists of participants age 18-80 years inclusive, with diagnosis of essential tremor of at least 3 years duration.*
7. *The outcome for the primary efficacy endpoint is mean change from baseline in clinic-based TETRAS performance subscale part 4 upper limb tremor score at Day 29.*
8. *The population-level summary measure is the difference in mean change from baseline in clinic-based TETRAS performance subscale part 4 upper limb tremor score of between the two groups (SAGE-324 and placebo).*

This will be analyzed using a mixed effects model for repeated measures (MMRM); the model will include treatment, baseline TETRAS performance subscale part 4 upper limb tremor score, assessment timepoint, and timepoint-by-treatment as explanatory variables. All

explanatory variables will be treated as fixed effects. All postbaseline clinic visits will be included in the model. The main comparison will be between SAGE-324 and placebo at the 29-day timepoint. Model-based point estimates (ie, least squares means, 95% confidence intervals, and p-values) will be reported where applicable. An unstructured covariance structure will be used to model the within-participant errors. The Kenward-Roger approximation will be used to estimate denominator degrees of freedom.

If there is a convergence issue with the unstructured covariance model, Toeplitz or Autoregressive (1) [AR(1)] covariance structure will be used, following this sequence until convergence is achieved. If the model still does not converge with AR(1) structure, no results will be reported. When the covariance structure is not unstructured, the sandwich estimator for the variance covariance matrix will be derived, using the EMPIRICAL option in the PROC MIXED statement in SAS.

For each model, the comparison of interest will be between SAGE-324 and matching placebo at Day 29 time point, with model-based point estimates (i.e., LS means), 95% confidence intervals, and p-values will be reported for all time points.

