APPENDIX C. LIST OF DISPLAYS

Tables

14.1.1	Disposition of Participants (All Subjects)
14.1.2	Analysis Sets (All Subjects)
14.1.3.1	Major Protocol Deviations (Safety Set)
14.1.3.2	Protocol Deviations Related to Covid-19 (Safety Set)
14.1.4.1	Demographics and Baseline Characteristics (Safety Set)
14.1.4.2	Demographics and Baseline Characteristics - Subgroups (Safety Set)
14.1.5	Summary of Disease History (Safety Set)
14.1.6	Medical/Surgical History (Safety Set)
14.1.7.1	Prior Medications (Safety Set)
14.1.7.2	Concomitant Medications (Safety Set)
14.1.8.1	Study Drug Exposure (Safety Set)
14.1.8.2	Study Drug Adherence (Safety Set)
14.2.1.1	Summary of Essential Tremor Rating Assessment Scale (TETRAS) Performance Subscale Part 4 Upper Limb Tremor Score (Full Analysis Set)
14.2.1.2	Change from Baseline in the Essential Tremor Rating Assessment Scale (TETRAS) Performance Subscale Part 4 Upper Limb Tremor Score – Mixed Effect Model for Repeated Measures (MMRM) (Full Analysis Set)
14.2.1.3.1	Change from Baseline in the Essential Tremor Rating Assessment Scale (TETRAS) Performance Subscale Part 4 Upper Limb Tremor Score – Sensitivity Analysis – Missing Data Imputation (Full Analysis Set)
14.2.1.3.2	Change from Baseline in the Essential Tremor Rating Scale (TETRAS) Assessment Performance Subscale Part 4 Upper Limb Tremor Score – Sensitivity Analysis – Excluding Subjects From Sites 001, 002, 003, 004, 007, 008, 010, 011, 017, 019, 021, 023, 024 (Full Analysis Set)
14.2.1.4	Summary of Essential Tremor Rating Assessment Scale (TETRAS) Performance Subscale Part 4 Upper Limb Tremor Score (Per Protocol Set)
14.2.1.5	Change from Baseline in the Essential Tremor Rating Assessment Scale (TETRAS) Performance Subscale Part 4 Upper Limb Tremor Score – Mixed Effect Model for Repeated Measures (MMRM) (Per Protocol Set)
14.2.1.6	Summary of Essential Tremor Rating Assessment Scale (TETRAS) Performance Subscale Part 4 Upper Limb Tremor Score by Subgroup, Total Score (Full Analysis Set)
14.2.1.7	Change from Baseline in the Essential Tremor Rating Assessment Scale (TETRAS) Performance Subscale Part 4 Upper Limb Tremor Score by Subgroup, Total Score - Mixed Effect Model for Repeated Measures (MMRM) (Full Analysis Set)
14.2.2.1	Summary of Essential Tremor Rating Assessment Scale (TETRAS) ADL (Full Analysis Set)

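### Subgroup pooling has no per-arm minimum, so a kept category of about 5 to 7 patients can be plotted with a confidence interval that is too narrow

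*SAP*

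**What the plan says.** SAP 8.3.3.1.5 lists ten subgroup factors with 28 categories in all. Its pooling rule begins "If any of the subcategories has <5 patients fall into that category, that category should be combined" and sends the category to a neighbouring one. The worked example is "if the number of patients fall into BMI category <18.5 is <5, this category should be combined with the 18.5 - <25 group". Neither mentions treatment arm, so a count over both arms together is the natural reading.

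Categories that are kept appear in forest plots for six scores: Part 4 left, right and combined, performance total, Parts 4/6/7/8, and ADL. The plot content ends with "ADL total score at Day 29 – LS means, confidence interval – will be provided". Appendix C lists matching model tables; Table 14.2.1.7 is titled in part "Upper Limb Tremor Score by Subgroup, Total Score - Mixed Effect Model for Repeated Measures (MMRM) (Full Analysis Set".

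The only MMRM rules are in SAP 8.3.3.1.1. Besides treatment, the model has "baseline TETRAS performance subscale part 4 upper limb tremor score, assessment timepoint, and timepoint-by-treatment as explanatory variables". Covariance is unstructured with Kenward-Roger degrees of freedom; if that does not converge, Toeplitz and then AR(1) are tried. In the fallback, "the sandwich estimator for the variance covariance matrix will be derived, using the EMPIRICAL option in the PROC MIXED statement in SAS". If AR(1) also fails, nothing is reported. No separate model, covariance or degrees-of-freedom rule is given for subgroups.

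**The concern.** A threshold on the total count allows a category of 5 with 3 vs 2 or 4 vs 1 patients, or even with an empty arm. A repeated-measures model with an unstructured covariance cannot be estimated from so few patients. The SAP's own fallback then applies a variance estimator that relies on many independent patients.

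With a handful of patients the sandwich variance is biased downward. The risk is that the rows with least information look the most precise, so that a reader of the forest plot takes noise in a tiny category for a subgroup effect.

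Sparse categories are plausible with about 60 randomized. For example, Protocol 8.1 (inclusion criterion 4) requires at least 1.5 on each of six items and at least 5.5 for the dominant limb. The lowest eligible Part 4 total is therefore 5.5 + 3 × 1.5 = 10, and the baseline category below 12 spans only 10 to 11.5 on a 0–24 scale.

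**Working it through.** **Inputs.** From SAP 5.2: SD 3.5, difference 3, 25 evaluable per arm, 1:1 allocation, about 60 randomized. From SAP 8.3.3.1.1: the model terms and covariance sequence. Assumed: one model per category, a singular unstructured fit counts as a convergence issue, correlation 0.6 between all visits, complete data, no treatment effect.

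**1. The plan's own figure.** SE = 3.5 × √(2/25) = 0.990, and 3/0.990 = 3.03. Power = Φ(3.03 − 1.96) = 85.8% (84.4% with the t distribution), which agrees with the stated 85%. Also 50/0.85 = 58.8, stated as about 60.

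**2. Arm split of a 5-patient category drawn from 30 + 30.**
- Empty arm: 2 × C(30,5)/C(60,5) = 2 × 142,506/5,461,512 = 5.2%.
- An arm with 0 or 1 patient: 2 × (142,506 + 30 × 27,405)/5,461,512 = 35.3%.
- At 6 patients these are 2.4% and 19%; at 8 patients, 0.5% and 5%.

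**3. Can the unstructured model be fitted?** After the arm-by-visit means are removed, n patients leave n − 2 independent residual vectors, each of length q visits. A full-rank q × q covariance needs at least q of them. When n − 2 = q, the single baseline slope can still be chosen to make the matrix singular. So n − 2 must exceed q: n ≥ 7 for four visits (Days 8 to 29) and n ≥ 8 for five (with Day 42). Simulated REML fits agree:

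| Visits | Split | Singular fits |
|---|---|---|
| 4 | 3+2 | 39/40 |
| 4 | 3+3 | 40/40 |
| 4 | 4+3 | 1/40 |
| 4 | 4+4 | 0/40 |
| 4 | 5+5 | 0/40 |
| 5 | 3+2 | 14/15 |
| 5 | 4+3 | 15/15 |
| 5 | 5+5 | 0/15 |

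**4. The sandwich fallback** (four visits; Day 29 arm difference; 400 runs for AR(1), 250 for Toeplitz; Monte Carlo error of coverage about 1 to 3 points).

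| Split | Structure | Sandwich SE / true SE | Coverage, residual df | Coverage, df n − 3 | Median half-width, residual df / n − 3 |
|---|---|---|---|---|---|
| 3+2 | AR(1) | 0.55 | 73.0% | 92.7% | 4.2 / 8.2 |
| 3+2 | Toeplitz | 0.52 | 72.4% | 91.2% | 4.2 / 8.3 |
| 4+1 | AR(1) | 0.32 | 53.5% | 74.8% | 2.9 / 5.7 |
| 3+3 | AR(1) | 0.59 | 74.3% | 89.2% | 4.2 / 6.3 |
| 4+4 | AR(1) | 0.77 | 85.5% | 91.5% | 4.0 / 5.0 |
| 5+5 | AR(1) | 0.86 | 87.7% | 92.2% | 3.8 / 4.4 |
| 5+5 | Toeplitz | 0.79 | 86.8% | 92.8% | 3.9 / 4.5 |
| 12+12 | AR(1) | 0.91 | 92.2% | 93.5% | 2.7 / 2.8 |

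With a repeat of the simulation included, the ranges at 3+2 are a ratio of 0.52–0.55 and coverage of 71–73% (residual df) or 90–93% (n − 3). At 4+1 they are 0.32–0.34, 51–54% and 75–77%.

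**5. Side by side in a forest plot.** Where the unstructured model fits, the median half-width (model-based SE, df n − 3) is 8.1 at 4+3, 6.2 at 4+4 and 5.2 at 5+5, with roughly nominal coverage in only 40 runs each. At 3+2 the sandwich interval has half-width 4.2 at residual df, against about 17 for a correct interval. At 4+1 it is 2.9, or 5.7 even at n − 3. These rows would look tighter than a 7-patient row.

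**The case against.** Several points on the other side stand.

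- **Scope.** A reader might infer that the forest plots will in general show intervals that are far too narrow. The documents do not support that. They give no subgroup counts, and from about 7 or 8 patients upward, where the unstructured model fits, the intervals are wide and roughly valid.
- **Parameter count.** A reader might also argue that the model has more parameters than data: 10 means + 1 baseline slope + 15 covariances = 26, against 5 × 5 = 25 values. That needs Day 42 in the model. SAP 8.3.3.1.1 takes all postbaseline clinic visits, but 8.3.2 calls Day 42 post-treatment. With four visits the count is 8 + 1 + 10 = 19 against 20. The fit still fails at 5 or 6 patients, but for the rank reason in step 3.
- **Separate fits.** The SAP does not say that each category gets its own model. One model on the whole Full Analysis Set with interaction terms is not ruled out and would avoid most of the problem. It is not specified either.
- **Degrees of freedom.** Kenward-Roger is named, but not how it applies with EMPIRICAL. The low coverage figures are for residual df; with n − 3, coverage at 3 vs 2 is 90–93%. At 4 vs 1 it stays near 75%.
- **Consequence.** No subgroup test or claim is planned. An empty arm is uncommon, and the arm difference is then simply not estimable.

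These points limit the size of the problem. They do not supply the missing per-arm minimum or subgroup model rule.

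**Conclusion.** The point holds in a limited form. The pooling rule has no per-arm minimum. If categories are fitted separately under 8.3.3.1.1, those with 5 or 6 patients (5 to 7 with Day 42) usually end in the sandwich fallback. The standard error is then understated by about half at 3 vs 2 and by about two-thirds at 4 vs 1, and the loss of coverage depends heavily on degrees of freedom that the SAP leaves open. The smallest categories can therefore look more precise than larger ones.

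The size rests on the assumed correlation of 0.6, complete data and separate models. Whether any kept category is this small cannot be known from the documents. Only the subgroup displays are affected. This is a cheap improvement worth making, not a threat to the trial's main conclusion.

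**What to change.** In SAP 8.3.3.1.5:

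1. Apply the pooling threshold per arm, for example at least 5 patients in each arm, otherwise pool. The 5 is a choice; at 5 + 5 the unstructured model fitted in 40 of 40 runs with four visits and 15 of 15 with five.
2. Where pooling cannot reach the minimum, as with the two-level factors, show descriptive statistics only. SAP 8.3.3 and Table 14.2.1.6 already plan these.
3. State how the subgroup models are fitted and whether Day 42 is included. One whole-FAS model with subgroup interaction terms is an acceptable option, not the only one.
4. Do not report uncorrected EMPIRICAL intervals from small subgroup fits. Use a model-based or small-sample-corrected variance and name the degrees of freedom. The per-arm minimum alone is not enough: if the fallback were used at 5 + 5, the SE ratio would still be 0.79–0.86 and coverage 87–93%.

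The cost is SAP wording and programming. Some small categories are merged or lose an interval. Per-arm counts are known only after unblinding, so the rule should be fixed in the SAP beforehand and applied mechanically.

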8.4. Safety Analysis

Safety and tolerability of SAGE-324 will be evaluated by adverse events, [REDACTED] Safety data will be listed by participant and summarized by treatment group.

For safety summary tables, the safety endpoints evaluated at scheduled visits are taken as done and nominal visit will be summarized as scheduled visits. For multiple values from the specific visit window, the choice of the visit record will be following the same rule as described in Section [Error! Reference source not found..](#)

All safety summaries will be performed on the Safety Set using treatment received. See [Table 4](#) for details on how safety endpoints will be presented.

No statistical hypothesis testing will be conducted on the safety data.

Table 4: Presentation of Safety Endpoints

Safety Evaluation	Incidence	Raw Value	Change from Baseline	Clinical Significance	Abnormality	Derived PCS values
AEs	X	*				

X = Safety Assessment will be summarized in tables
* = Safety Assessment will be presented in individual participant data listings
Note: Clinical significance and abnormality are based on Investigator review and collected directly from the eCRF.
Note: PCS = Potentially Clinically Significant.

8.4.1. Adverse Events

Adverse events (AEs) will be coded using MedDRA Version 22.1 or higher. In the event of a missing/incomplete start or stop date associated with an adverse event, only the treatment-emergence will be imputed using the algorithm described in [Appendix B](#). Dates will not be imputed.

A TEAE is defined as an AE with onset at or after the start of IP, or any worsening of a preexisting medical condition/AE with onset at or after the start of IP and throughout the study. The term IP includes both SAGE-324 and placebo. Summary tables of AEs will include TEAEs only.

An overall adverse event summary table will be presented for TEAEs and will include the number and percent of participants experiencing at least one:

- TEAE
- Maximum severity of TEAE (mild TEAE, moderate TEAE, severe TEAE)
- TEAE leading to study treatment discontinuation
- TEAE leading to study discontinuation
- Serious TEAE
- Serious TEAE leading to study treatment discontinuation
- Serious TEAE leading to study discontinuation
- TEAE resulting in death

[figure not shown]
The incidence of TEAEs will be summarized by System Organ Class (SOC) and PT. In addition, summaries will be provided by maximum severity (mild, moderate, severe) and by maximum relationship (related, not related) to IP. Any TEAEs leading to discontinuation of treatment or withdrawal from the study and any treatment-emergent serious adverse events (SAEs) will also be summarized, sorted by descending frequency in SOC and PT within the SAGE-324 group.

[figure not shown]
[figure not shown]
Participants will be counted only once within each SOC and PT at the maximum severity in the following order: severe, moderate, and mild. Participants will be counted only once within each SOC and PT at the strongest relationship to study drug in the following order: related, not related to study drug. An AE with missing severity will be considered as ‘severe’, and with missing relationship to study treatment will be considered as ‘related’ for the purposes of summarizing these data.

[figure not shown]
The incidence of TEAEs and treatment-emergent SAEs will also be presented in order of decreasing frequency by PT only within the SAGE-324 group.

[figure not shown]
All AEs and SAEs (including those with onset or worsening before the start of investigational product) through the end of the study will be listed. In addition, separate listings containing individual participant AE data for all deaths, SAEs, AEs leading to treatment discontinuation, and AEs leading to study discontinuation will be provided.

[figure not shown]

[figure not shown]
[figure not shown]

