2. SYNOPSIS

Name of Sponsor/Company: Sage Therapeutics, Inc. (hereafter referred to as Sage Therapeutics, or Sage)																
Name of Investigational Product: SAGE-324 Oral Tablet																
Name of Active Ingredient: SAGE-324																
Title of Study: A Phase 2, Double-blind, Placebo-controlled, Randomized Study Evaluating the Efficacy, Safety, and Tolerability of SAGE-324 in the Treatment of Individuals with Essential Tremor																
Number of Sites and Study Location: This study will take place at approximately 30 sites in the United States.																
Phase of Development: Phase 2																
Planned Duration for each Study Participant: The duration of participation (from Screening through the final follow-up visit) for each participant is estimated to be up to 71 days.																

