8. SELECTION AND WITHDRAWAL OF PARTICIPANTS

8.1. Participant Inclusion Criteria

Participants must meet all of the following criteria to qualify for participation in this study:

1. Participant has signed an ICF before any study-specific procedures or washout of drugs is performed.
2. Participant is ambulatory and is 18 to 80 years of age, inclusive, at the time informed consent is obtained.
3. Participant has a diagnosis of ET, as defined by all of the following criteria:
 - a. Isolated tremor syndrome consisting of bilateral upper limb action tremor
 - b. At least 3 years duration
 - c. With or without tremor in other locations (eg, head, voice, or lower limbs)
 - d. Absence of other neurological signs, such as dystonia, ataxia, or parkinsonism, isolated focal tremors (eg, voice, head), task- and position-specific tremors, sudden tremor onset or evidence of stepwise deterioration of tremor
4. Participant scores at least 1.5 for each of the six items that comprise the combined total upper limb TETRAS (total performance subscale part 4) with the total score for the dominant upper limb (the sum of the three items for either the right or left upper limb, whichever is dominant) being at least 5.5, at both Screening and predose on Day 1.
5. Participant is willing to completely downtitrate and discontinue from medications taken for the treatment of ET at least 14 days or 5 half-lives (whichever is longer) prior to receiving IP. Medications taken for the treatment of ET that were discontinued prior to receiving IP may be resumed following Day 29.
6. Participant is willing to discontinue the use of alcohol and products that contain nicotine within at least 1 week prior to Day 1 and through Day 29 of the study.
7. Female participant agrees to use at least one method of highly effective contraception as listed in Section [9.2.4](#) during participation in the study and for 30 days following the last dose of study drug, unless she is postmenopausal (at least 12 months of spontaneous amenorrhea without an alternative medical cause, with confirmatory follicle stimulating hormone >40 mIU/mL), and/or surgically sterile (bilateral oophorectomy, hysterectomy, and/or bilateral salpingectomy), or does not engage in sexual relations which carry a risk of pregnancy (does include abstinence).

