13.6.1. Adverse Events

AEs will be coded using Medical Dictionary for Regulatory Activities (MedDRA) Version 22.1 or higher. A treatment-emergent adverse event (TEAE) is defined as an AE with onset after the first dose of IP. The analysis of AEs will be based on the concept of TEAEs. The incidence of TEAEs will be summarized by System Organ Class (SOC) and preferred term. In addition, summaries will be provided by intensity (mild, moderate, severe) and by causality (related, not related) to IP.

[figure not shown]
Any TEAEs leading to discontinuation of treatment or withdrawal from the study and any treatment-emergent SAEs will be summarized.

All AEs and SAEs (including those with onset or worsening before the start of IP) through the end of the study will be listed.

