During the follow-up period, visits will be conducted on an outpatient basis. In addition to the phone calls to review current status, participants will receive a phone call approximately 7 days after the last dose of IP (ie, Day 35) for safety monitoring. Participants will return to the study center for an end of study visit approximately 14 days following the last dose of IP (ie, Day 42).

Figure 1: Study Design

Abbreviation: EOT = end of treatment

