8.2. Background Characteristics

8.2.1. Participant Disposition

The summaries of disposition will include the number of participants who were screened, who were randomized, who received study drug, the number and percentage of participants who completed the study and who prematurely withdrew from the study, primary reasons for not completing the study, who completed treatment, who discontinued treatment prematurely, and primary reasons for discontinuing treatment. Study completion summary and treatment completion summary will be based on participants who received study drug (Safety Set). Percentages will be calculated based on the participants randomized and dosed. These data will be provided by randomized treatment groups. If a participant is rescreened because he/she has been a screen failure the first time, the status of the participant will be determined from the second screening. In the count of screened participants, this participant will be counted only once.

The number of participants in each of the analysis sets will also be summarized and presented by the randomized treatment.

A completer for the study is defined as one who completed the final follow-up visit and is derived from the Study Disposition CRF page with completion question answered Yes. A participant is defined as prematurely discontinuing treatment if treatment ends before the final dose of study drug is taken on Day 28, and is derived from the End of Treatment CRF page with completion question answered No. The main reason is provided in the same CRF page.

Randomization data (date and time of randomization, randomization number, and randomized treatment) and participants excluded from each analysis set will be listed but not summarized.

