8.2.5. Prior and Concomitant Medications

Medications will be recorded at each study visit and coded into drug class (anatomical therapeutic chemical [ATC] Level 2) and PT using World Health Organization-Drug dictionary (WHO-DD) Global B3 September 2019, or later.

All medications taken within 30 days prior to informed consent through the duration of the study (including start and end dates, route, dose/units, frequency, and indication) will be recorded on the electronic case report form (eCRF); all psychotropic medications taken in the 30 days prior to screening will also be recorded. Those medications taken prior to the initiation of the investigational product will be denoted “Prior”. Those medications taken prior to the initiation of the investigational product and continuing beyond the initiation of the investigational product or those medications started at the same time or after the initiation of the investigational product will be denoted “Concomitant”. Note that medication taken before the initial dosing of investigational product and continued after the initial dosing will be categorized as a prior medication and separately as a concomitant medication.

Medications will be flagged in the listing according to whether they are “Prior” or “Concomitant” as defined above. In the event of a missing start or stop date associated with a medication, only the classification (prior and/or concomitant) will be imputed using the algorithm described in [Appendix B](#). Dates will not be imputed.

Details of prior and concomitant medications will be listed by participant, start date, and verbatim term. Prior and concomitant medications will be summarized separately for the Safety Set as the number and percentage of participants with each medication at both the ATC and PT levels.

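### The adverse event tables use a single window to about Day 42, so events on SAGE-324 are not separated from events after it is stopped

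*SAP*

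**What the plan says.** SAP 8.4.1 takes as treatment-emergent (TEAE) an AE that begins at or after the first dose, or "any worsening of a preexisting medical condition/AE with onset at or after the start of IP and throughout the study". It adds: "Summary tables of AEs will include TEAEs only". Protocol (Amendment 4) 13.6.1 sets no end point either: a TEAE "is defined as an AE with onset after the first dose of IP". TEAE incidence is the only safety endpoint legible in SAP 4.2.

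For dosing, SAP 8.2.1 classes a participant as stopping early if "treatment ends before the final dose of study drug is taken on Day 28". SAP 5.1 schedules an "end of study visit approximately 14 days following the last dose of IP (ie, Day 42").

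For other treatment, inclusion criterion 5 (Protocol 8.1) states: "Medications taken for the treatment of ET that were discontinued prior to receiving IP may be resumed following Day 29". Medications are recorded to the Day 42 visit (Protocol 9.2.1). SAP 8.2.5 says that "those medications started at the same time or after the initiation of the investigational product will be denoted" concomitant, with no end bound at the last dose.

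SAP Appendix C lists AE Tables 14.3.1.1 to 14.3.1.9 and one concomitant medication table, 14.1.7.2. No title mentions an on-treatment or post-treatment period.

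**The concern.** The 28 days of dosing show how SAGE-324 is tolerated. The 14-day follow-up shows what happens after it is stopped. A single TEAE window merges the two. A participant with an event on Day 10 and one with the same event on Day 38, ten days after the last dose and perhaps on a restarted ET drug, count identically. SAP 8.4.1 also counts each participant once per term at maximum severity. A mild event on drug followed by a severe one in follow-up therefore appears as one severe TEAE, with no indication of timing.

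This matters because tolerability on drug is a live question here. Protocol 5.2 already treats somnolence as an adverse drug reaction, and Protocol 7.4 requires dose interruption and reduction for somnolence-type events. Readers will want on-drug incidence by arm, and separately what followed stopping. The planned tables give neither directly.

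**Working it through.** **Inputs.** Last planned dose Day 28 (SAP 8.2.1). End of study Day 42 (SAP 5.1), visit window ±1 day (Protocol Table 2). Screening up to 28 days, a 29-day treatment period and 14 days of follow-up (Protocol 7.1). ET drugs permitted from Day 30 (Protocol 8.1). After early stopping: an EOT visit, a call 7 days later and a final visit 7 days after that (Protocol 8.4.1).

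**1. The plan's own calendar.** 28 + 14 = Day 42 and 28 + 7 = Day 35, both as stated. The Protocol synopsis says participation "for each participant is estimated to be up to 71 days", and 28 + 29 + 14 = 71. Counting study days gives 28 + 42 = 70, because Day 29 lies in both the treatment period and the 14 days after the last dose. Nothing below depends on that day.

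**2. Off-drug share, completer.** (42 − 28)/42 = 14/42 = 33.3%. With the visit window it is 13/41 = 31.7% to 15/43 = 34.9%.

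**3. Days when restarted ET drugs are permitted, completer.** Days 30 to 42 are 13 of the 14 off-drug days.

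**4. Early stoppers.** With last dose on Day L and 14 days of follow-up, the off-drug share is 14/(L + 14):
- L = 21: 14/35 = 40%
- L = 14: 14/28 = 50%
- L = 7: 14/21 = 67%

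The share is higher still if the EOT visit falls some days after the last dose. Permitted ET-drug resumption stays tied to Day 29. It covers Days 30 to 35 when L = 21, and no days when L is 15 or earlier.

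**5. Could the mixing change the picture?** The documents give no AE rates, so this is illustration only. Assume 28-day incidence q on placebo and p on SAGE-324, a constant background hazard, and an off-drug hazard in the SAGE-324 arm of m times background.
- Placebo to Day 42: 1 − (1 − q)^(42/28)
- SAGE-324 to Day 42: 1 − (1 − p)(1 − q)^(14m/28)

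For q = 30%, p = 60%, m = 1: placebo 41.4%, SAGE-324 66.5%, difference 25.1 points, against 30 points on drug. With m = 2: SAGE-324 72.0%, difference 30.6 points.

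| q | p | Difference to Day 28 | To Day 42, m = 1 | To Day 42, m = 2 |
|---|---|---|---|---|
| 20% | 50% | 30 | 26.8 | 31.6 |
| 20% | 60% | 40 | 35.8 | 39.6 |
| 30% | 50% | 20 | 16.7 | 23.6 |
| 30% | 60% | 30 | 25.1 | 30.6 |
| 40% | 50% | 10 | 7.7 | 16.5 |
| 40% | 60% | 20 | 15.5 | 22.5 |

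With m = 1 the difference shrinks by 2.3 to 4.9 points. With m = 2 it moves by −0.4 to +6.5 points. Neither the sign nor the size is determined, and a pooled table cannot tell the two situations apart.

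**The case against.** The strongest reply is that nothing here is an error. Counting TEAEs through a safety follow-up is an accepted convention. It captures late and residual drug reactions, and it matches Protocol 12.2.1 and 13.6.1. That stands: the overall count should stay.

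The plan also has partial separators. There is a related/not-related summary, a table of TEAEs leading to treatment discontinuation (14.3.1.5), a listing of AEs leading to dose reduction or discontinuation (14.3.2.3), and listings of all AEs. Laboratory, ECG and vital-sign summaries go by visit, so Day 42 is already distinct from Day 29. These help, but relatedness is investigator judgement rather than timing, the discontinuation displays cover only events that changed dosing, and listings give no incidence by arm.

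Parts of the safety sections are redacted, so a post-treatment display elsewhere cannot be excluded. The AE tables themselves are numbered without a gap, so none is hidden among them.

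Three stronger readings are tempting, and the documents do not support them:
- A reader might infer that the pooled window dilutes the relative risk. That needs assumed rates, the direction depends on those assumptions, and the plan reports counts and percentages with no hypothesis testing of safety data (SAP 8.4).
- A reader might infer that ET-drug use before the Day 29 rating would go unseen. Such use breaches Protocol 9.2.2, non-permitted medications are recorded (Protocol 8.4.2), major deviations are reviewed before unblinding (SAP 8.2.2), and medications are listed by participant and start date (SAP 8.2.5).
- A reader might infer that withdrawal events are expected. The legible text reports none and gives no half-life, so some early post-dose events could still be drug reactions.

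**Conclusion.** The point holds as a gap in presentation, not as an error in the TEAE definition. One third of a completer's AE window is off drug, and 40% to 67% for last doses between Day 21 and Day 7, assuming 14 days of follow-up after the last dose. The legible AE tables do not show that division. How much this would alter the safety picture, and in which direction, cannot be established from the documents. Placebo participants may also restart ET drugs, so effects of resumed treatment need not favour either arm.

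The change is worth making because it is cheap and answers two questions that the pooled tables leave open. It has no bearing on the Day 29 primary analysis, alpha or power.

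**What to change.** In SAP 8.4.1, keep the overall TEAE column and add on-treatment and post-treatment columns per arm to Tables 14.3.1.1 to 14.3.1.3:
- Split at each participant's own last dose of IP, not at a fixed study day.
- If a residual-exposure margin is added after the last dose, pre-specify it, with the sponsor justifying its length from PK data. The legible text supports no particular margin.
- Count drug-holiday days before the last dose as on-treatment.
- State that a participant with events in both periods appears in both columns, so the columns need not add to the overall figure.
- Add a rule to Appendix B for onset dates too incomplete to place relative to the last dose.

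Optionally, flag in Table 14.1.7.2 the ET drugs first retaken after the Day 29/EOT rating.

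AE onset date and time (Protocol 12.2.5) and medication start and end dates (Protocol 9.2.1) are already collected. The cost is SAP wording, derived period flags and wider tables.
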